All subjects aged 12 years and older, with at least 365 days of data availability before index date (ID) [ID defined as the date of the latest vaccine dose administered] AND data availability from 12/2020 onwards (i.e. the time when the roll-out of the vaccination campaign started) in the respective database will be included.

	Phase II C3-002 – Study Protocol							
	Author(s): [name], [name], [name]				Version: v2.1			
	Dissemination level: Public							

All studies will be carried out comparing the following cohorts, which we defined based on varying degrees of vaccine exposure and period of predominant SARS-CoV-2 variant as shown in Table 1 below.

COVID-19 vaccination history	Cohort number							
	1	2	3	4	5	6	7	8
1 dose only					x			
Complete primary vaccination course (monovalent only)	x	x	x	x		x	x	x
3rd dose, also called 1st booster (monovalent or any of the adapted, bivalent)	x	x	x	x			x	x
4th dose, also called 2nd booster (monovalent or any of the adapted, bivalent)		x						x
4th dose, also called 2nd booster (any of the monovalent)			x					
4th dose, also called 2nd booster (any of the adapted, bivalent boosters)				x				
Study period								
Start of roll-out 4 th dose/2 nd booster onwards	x	x	x	x				
XBB variant or later dominant	x	x	x	x				
Any variant dominant					x	x	x	x

*Cohorts 3 and 4 will only be created for databases where the vaccine product is reliably recorded in addition to vaccine brand.

Outcomes 1-2 will be assessed in cohorts 1-2 (and 3-4 where available), outcomes 3-7 will be assessed in cohorts 5-8.

Unvaccinated groups will not be used as a comparator in our study for vaccine effectiveness research because they may be very different from vaccinated individuals regarding their risk of infection with SARS-Cov-2. This study therefore focusses on the association of varying degrees of vaccine exposure and COVID-19 related outcomes.

Study period:

Period of “start of roll-out 4th dose/2nd booster dose onwards”: from 01/08/2022 - last available data for each database.

Period of “XBB variant or later dominant”: 01/03/2023 - last available data for each database. Note: This period is not covered by any of the data cuts onboarded for DARWIN EU at the time of protocol submission.

Period of “any variant dominant”: 01/01/2021 (when the wider roll-out of the vaccination campaign started) - last available data for each database.

Statistical analyses:

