Hazard ratios will be calculated for subsequent time windows after index date, i.e. in bi-weekly intervals.

Monthly intervals will be used in case of small event counts to increase sample size and power if needed.

Kaplan-Meier plots and/or cumulative incidence plots will be used to illustrate survival analyses.

Objectives 3-6: Post-acute COVID-19 complications

The following comparisons will be conducted for objectives 3-6:

- First-dose vaccinated vs. second-dose vaccinated [cohort 5 vs. 6]
- Second-dose vaccinated vs. 3rd dose vaccinated (1st booster dose) [cohort 6 vs 7]
- 3rd dose vaccinated vs. 4th dose vaccinated (2nd booster dose) [cohort 7 vs 8]

Objective 3 will be assessed for SIDIAP and IPCI only, whereas objectives 4-6 will be assessed in CPRD, IPCI and SIDIAP.

Study population

The study populations will be derived similar to the inclusion process outlined for objectives 1-2 above, including sequential matching.

For objectives 4 and 5, people with the respective outcome recorded anytime in their history will be excluded for the respective objective. For objective 6, an outcome-free washout window of 365 days prior to index date will be implemented.

Outcomes:

- COVID-19 hospitalization + death within 3/6 months from discharge
- SARS-CoV-2 infection + New onset diabetes Type 1 diabetes within 30-365 days after COVID-19
- SARS-CoV-2 infection + New onset diabetes Type 2 diabetes within 30-365 days after COVID-19
- SARS-CoV-2 infection + cardiovascular events (ccar) in the 12 months after a SARS-CoV-2 infection

	Phase II C3-002 – Study Protocol	
	Author(s): [name], [name], [name]	Version: v2.1
		Dissemination level: Public

For contextualization and interpretation of the study findings, we will also report the number of people with COVID-19 hospitalization and SARS-CoV-2 infections in each group, as these are part of the overall outcomes of “death following discharge from COVID-19 hospitalisation” and post COVID-19 complications.

Vaccine effectiveness analyses for COVID-19 related mortality following hospital discharge:

Incidence rates will be calculated for the matched cohorts and outcome. Cox proportional hazard models will be calculated for each outcome to provide HR. Negative control outcomes will be used as an additional measure to measure residual confounding. In the scenario of potential unmeasured confounding being detected by NCO, empirical calibration²⁵ for HR might be considered to minimise bias.

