6. RATIONALE AND BACKGROUND

	Phase II C3-002 – Study Protocol	
	Author(s): [name], [name], [name]	Version: v2.1
		Dissemination level: Public

The research agenda of the Vaccine Monitoring Platform jointly coordinated by EMA and the European Centre for Disease Prevention and Control (ECDC) includes the continuous assessment of COVID-19 vaccine effectiveness.

COVID-19 vaccines were authorised for use in the European Union. These vaccines, and any (future) adapted vaccines, would therefore benefit from post-authorisation studies to provide real world evidence to guide regulatory and vaccination policies. A recent post-authorisation study performed in the Nordic countries, where near real-time data is available, showed that receipt of a bivalent BA4/5 mRNA booster as a fourth dose provides 67.8% protection against COVID-19 related hospitalisation⁴. There is also evidence that effectiveness starts to wane after a few months. For regulatory purposes, such data are especially useful for the most recent variants, including XBB and later.

There is mounting evidence on the occurrence of longer-term outcomes of SARS-CoV-2 infection⁵. This can include very specific outcomes such as cardiovascular events or the incidence of new-onset diabetes, or broader definitions such as the WHO clinical case definition for post COVID-19 condition⁶. Data are needed regarding the COVID-19 vaccines effectiveness at preventing these outcomes. This is pertinent for the most recent COVID-19 variants, but equally important for older variants.

The EMA has therefore requested a study to evaluate the effectiveness of Comirnaty and Spikevax against severe COVID-19 outcomes and post-acute outcomes of SARS-CoV-2 infection.

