7. RESEARCH QUESTION AND OBJECTIVES

Research Question

What is the effectiveness of the EMA-authorized COVID-19 vaccines Comirnaty and Spikevax against severe COVID-19 and post-acute outcomes of SARS-CoV-2 infection?

Objective(s)

To generate additional evidence on the effectiveness of COVID-19 vaccines at preventing severe COVID-19 and post-acute outcomes of SARS-CoV-2 infection.

Specifically, this study has 6 objectives:

1. To assess the effectiveness of COVID-19 vaccination for the prevention of severe COVID-19 related outcomes (COVID-19 related hospitalisation or COVID-19 related death)
2. To assess waning of the effectiveness of COVID-19 vaccination for the prevention of severe COVID-19 related outcomes (COVID-19 related hospitalisation or COVID-19 related death)
3. To assess the effectiveness of COVID-19 vaccination for the prevention of all-cause mortality in the 3- and 6-months following discharge for COVID-19 related hospitalisation
4. To assess the effectiveness of COVID-19 vaccination for the prevention of new-onset type 1 Diabetes Mellitus in the 12 months after a SARS-CoV-2 infection
5. To assess the effectiveness of COVID-19 vaccination for the prevention of new-onset type 2 Diabetes Mellitus in the 12 months after a SARS-CoV-2 infection
6. To assess the effectiveness of COVID-19 vaccination for the prevention of cardiovascular events in the 12 months after a SARS-CoV-2 infection

	Phase II C3-002 – Study Protocol	
	Author(s): [name], [name], [name]	Version: v2.1
	Dissemination level: Public	

Table 7.1: Primary and secondary research questions and objective

A. Primary research question: Objectives 1-2

Objective:	To assess the effectiveness and waning of effectiveness of COVID-19 vaccination for the prevention of severe COVID-19 related outcomes
Hypothesis:	NA
Population (mention key inclusion-exclusion criteria):	All subjects aged 12 years and older, with at least 365 days of data availability in the respective database before index date (ID) with 
 • a 3rd-vaccine dose (1st booster dose) of Comirnaty or Spikevax. • at least 365days of data availability in the respective database • at least 90days of time elapsed since the last vaccine dose (i.e. the 3rd vaccine dose or 1st booster) at the time of study inclusion • at least 90days of time elapsed since the last record of a clinical diagnosis of COVID-19 or positive SARS-COV-2 test at the time of study inclusion.

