Exposure:	4 th vaccine dose/2 nd booster dose of Comirnaty or Spikevax
Comparator:	No 4 th vaccine dose/2 nd booster dose (only 3 rd dose)
Outcome:	COVID-19 related hospitalisation;COVID-19 related death
Time (when follow up begins and ends):	Follow-up start: at index date of matched 3-dose vaccinated/4-dose vaccinated people after start of roll-out of vaccination programs for 2nd booster dose End of follow-up: End of their observation (i.e. date of data extraction, database availability or death), next vaccine dose or outcome event, whatever comes first.
Setting:	Primary care electronic health records from SIDIAP [Spain], IPCI [The Netherlands] and CPRD GOLD [UK]
Main measure of effect:	Vaccine effectiveness, calculated as 1 - Hazard ratio (HR)

B. Primary research question: Objectives 3

	Phase II C3-002 – Study Protocol	
	Author(s): [name], [name], [name]	Version: v2.1
	Dissemination level: Public	

Outcome:	To assess the effectiveness of COVID-19 vaccination for the prevention of post-acute all-cause mortality in the 3- and 6-months following discharge for COVID-19 related hospitalisation
Hypothesis:	NA
Population (mention key inclusion-exclusion criteria):	All subjects aged 12 years and older, with at least 365 days of data availability in the respective database before index date (ID) with 
 • a 1st-vaccine dose [2nd vaccine dose; 3rd vaccine dose] of Comirnaty or Spikevax. • at least 365days of data availability in the respective database. • at least 90days of time elapsed since the last vaccine dose at the time of study inclusion. • at least 90days of time elapsed since the last record of a clinical diagnosis of COVID-19 or positive SARS-COV-2 test at the time of study inclusion.
Exposure:	2 nd vaccine dose [3 rd vaccine dose; 4 th vaccine dose] of Comirnaty or Spikevax
Comparator:	No 2 nd vaccine dose [3 rd vaccine dose; 4 th vaccine dose] of Comirnaty or Spikevax
Outcome:	All-cause mortality within 3/6months following COVID-19 related hospitalisation

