Country	Name of Database	Justification for Inclusion	Health Care setting	Type of Data (EHR, claims, registries)	Number of active subjects	Feasibility count of outcome/exposure (if relevant)	Data lock for the last update	Contributing to objectives
United Kingdom	CPRD GOLD	Complete records on SARS-CoV-2 infection, Covid-19 vaccination, and outcome events of interest (excl. hospitalization for COVID-19)	Primary care	EHR	3M	Covid-19: 360,198 Comirnaty: 2,822,947 Spikevax: 311,069	01/2023	1-2 for outcome “COVID-19 related death” only, 4-6
The Netherlands	IPCI	Complete records on SARS-CoV-2 infection, Covid-19 vaccination, and outcome events of interest	Primary care	EHR	1.39M	Covid-19: 941,329 Comirnaty: 1,173,104 Spikevax: 463,315	12/2022	1-6
Spain	SIDIAP	Complete records on SARS-CoV-2 infection, Covid-19 vaccination, and outcome events of interest; Include inpatient admission information.	Primary care + linkage to hospital data	EHR	5.8M	Covid-19: 3,865,976 Comirnaty: 6,548,545 Spikevax: 3,371,395	06/2022	1-6

	Phase II C3-002 – Study Protocol	
	Author(s): [name], [name], [name]	Version: v2
		Dissemination level: Public

Clinical Practice Research Datalink GOLD, United Kingdom (University of Oxford)

The Clinical Practice Research Datalink (CPRD) is a governmental, not-for-profit research service, jointly funded by the National Institute for Health and Care Research and the Medicines and Healthcare products Regulatory Agency, a part of the Department of Health, United Kingdom (UK) (<https://cprd.com>). CPRD GOLD¹¹ comprises computerized records of all clinical and referral events in primary care in addition to comprehensive demographic information and medication prescription data in a sample of UK patients (predominantly from Scotland (52% of practices) and Wales (28% of practices). The prescription records include information on the type of product, date of prescription, strength, dosage, quantity, and route of administration. Data from contributing practices are collected and processed into research databases. Quality checks on patient and practice level are applied during the initial processing. Data are available for 20 million patients, including 3.2 million currently registered patients. Approval for this study was granted via the Research Data Governance Process.

Integrated Primary Care Information Project (IPCI), The Netherlands (Erasmus)

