8.8.3 Objectives 1-2: Vaccine effectiveness to prevent severe infection

Objectives 1 and 2 will assess the effectiveness of a 4th COVID-19 vaccine dose in people with 3 vaccine doses.

Study population

All people with a 3rd vaccine dose of Comirnaty or Spikevax will be included from the source population. Cohorts will be generated separately for Comirnaty and Spikevax, respectively.

Study inclusion: Sequential matching

Inclusion will be conducted using a sequential matching design, with similar designs being used in previous studies assessing vaccine effectiveness. Previous research showed matching to adequately reduce measured confounding in vaccine effectiveness research when including key variables such as geographic location²⁴.

Matching process using key confounders and Propensity Scores

For each calendar week starting from the day when a 4th vaccine dose (i.e. 2nd booster vaccine) became available/recommended in the respective country, people will be assigned to two cohorts: people who received a 4th vaccine dose during that week and people who did not receive a 4th dose.

Using the first day of the respective week as “preliminary” index date for non-boostered people, and the date of the 4th dose for booster-vaccinated people, the following inclusion criteria will be applied:

	Phase II C3-002 – Study Protocol	
	Author(s): [name], [name], [name]	Version: v2.1
		Dissemination level: Public

- At least 365 days of data availability in the respective database
- At least 90days of time elapsed since the previous vaccine dose (i.e. the 3rd or 4th vaccine dose)
- At least 90days of time elapsed since the last record of a clinical diagnosis of COVID-19 or positive SARS-COV-2 test.

Among those people in the cohorts who received or not received a 4th dose and met the inclusion criteria, non-boostered people will be matched 1:1 to a person receiving their 4th dose, based on key confounders and large-scale propensity scores using nearest neighbor matching, with caliper width 0.2 standard deviation. Key confounders will comprise but are not limited to:

- Age (e.g. 5-year age bands)
- Sex (exact)
- Geographic location (exact)
- Previous vaccine brands (e.g. homologous or heterologous vaccination scheme)
- Time from previous vaccination
- History of conditions for prioritization for vaccination
- immunocompromised status
- previous SARS-CoV-2 diagnosis (>90days before index date)

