Objective 1: Vaccine effectiveness

Cox proportions hazard models will be used to calculate hazard ratios (HR) for the outcomes of COVID-19 related hospitalisation and COVID-19 related death.

Negative control outcomes will be used as an additional measure to measure any potential residual confounding. NCO are outcomes not causally associated with the exposure of interest²⁶, here COVID-19 vaccination. However, their association with vaccination is ideally impacted by the same type of unmeasured confounding, e.g. healthcare-seeking behavior, as the vaccination-outcome association²⁷. In the scenario of potential unmeasured confounding being detected by NCO, empirical calibration²⁵ for HR might be considered to minimise bias.

Vaccine effectiveness will be calculated as $1 - HR$. Kaplan Meier plots and/or cumulative incidence plots will be used to illustrate survival analyses.

The proportional hazard assumption will be tested visual investigation of log(-log) plots. In the scenario of substantial violation of the proportional hazard assumptions, alternative models/model adaptations will be used.

Objective 2: Waning of vaccine effectiveness

Hazard ratios will be calculated for subsequent time windows after index date, i.e. in bi-weekly intervals. Monthly intervals will be used in case of small event counts to increase sample size and power if needed. Vaccine effectiveness will be calculated as $1 - HR$.

Kaplan Meier plots and/or cumulative incidence plots will be used to illustrate survival analyses.

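### Objective 2 asks about waning, but section 8.8.3 plans only window-specific hazard ratios and gives no estimate or confidence interval for the change in effect with time since the 4th dose

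*Protocol*

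**What the plan says.** Objective 2 stands on its own in section 7: "To assess waning of the effectiveness of COVID-19 vaccination for the prevention of severe COVID-19 related outcomes". Table 7.1 A places it with Objective 1 under a primary research question, gives the hypothesis as not applicable and the main measure of effect as 1 - HR. The comparator is people with three doses and no fourth.

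The method is in section 8.8.3 under Objective 2: "Hazard ratios will be calculated for subsequent time windows after index date, i.e. in bi-weekly intervals". The abstract and 8.8.3 both add: "Monthly intervals will be used in case of small event counts to increase sample size and power if needed". VE is 1 - HR in each window, and Kaplan-Meier or cumulative incidence plots illustrate the results.

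No section plans a trend, an exposure-by-time term, a ratio of HRs or an early-versus-late comparison. The nearest item is a visual check of log(-log) plots, stated under Objective 1. It treats non-proportional hazards as an assumption violation to be handled by unspecified alternative models.

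**The concern.** A set of window HRs answers whether four doses did better than three in each window. Waning asks whether that advantage shrinks from one window to the next. Without an estimate of the shrinkage, readers are left to compare intervals by eye, and the usual shortcut is that VE was significant early and no longer significant later.

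That shortcut misleads when later windows hold fewer events, and three features of the plan point that way. Both members of a pair are censored when either one is, including when the comparator receives a 4th dose (8.8.3). The period for Objectives 1-2 runs "from 01/08/2022 - last available data for each database", and the data locks listed in Table 8.2.1 fall soon after that start. Pairs matched late reach only the early windows. Splitting by database, brand and age thins the counts further. A constant effect could then be reported as waning, and real waning could be left unquantified.

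**Working it through.** The protocol states no event count, power or alpha, so it has no figure of its own to reproduce. Event totals, the five-fold decline and the two-sided 5% level below are assumptions.

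**Inputs from the protocol.** Start 01/08/2022; data locks 01/2023 (CPRD GOLD), 12/2022 (IPCI), 06/2022 (SIDIAP). Matching is 1:1: "non-boostered people will be matched 1:1 to a person receiving their 4th dose". The only VE figure is from a cited Nordic study: "receipt of a bivalent BA4/5 mRNA booster as a fourth dose provides 67.8% protection against COVID-19 related hospitalisation", so HR = 1 - 0.678 = 0.322. VE 50% is added as an assumed lower value.

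**Number of windows.** To the end of 01/2023 is 184 days: 184/14 = 13.1, so about 13 bi-weekly windows. To the end of 12/2022 is 153 days: 153/14 = 10.9, so 10 complete ones. The listed SIDIAP lock precedes the start. These are maxima, reached only by the earliest pairs.

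**Events for one window to be significant** (80% power, two-sided 5%, 1:1): D = 4(1.960 + 0.842)² / (ln HR)².
- VE 67.8%: 31.4 / 1.133² = 24.4, so 25 events.
- VE 50%: 31.4 / 0.693² = 65.3, so 66 events.

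**Simulation** (40,000 runs). Poisson events a (no 4th dose) and b (4th dose) per window, 0.5 added to each; log HR = ln(b/a), variance 1/a + 1/b. A window is significant if its upper 95% limit is below 0. The trend contrast is the inverse-variance weighted slope of log HR on time, rejecting if |z| > 1.96.

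Constant effect, 13 windows, events falling five-fold from first to last:

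| Total events | Events in first / last window | VE 67.8%: first significant, last not | Trend rejects | VE 50%: first significant, last not | Trend rejects |
|---|---|---|---|---|---|
| 300 | 46 / 9 | 80% | 4% | 57% | 4% |
| 600 | 91 / 18 | 46% | 5% | 68% | 4% |
| 1,200 | 183 / 37 | 12% | 5% | 50% | 5% |

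At VE 67.8% the reverse pattern (last significant, first not) occurs in at most 1% of runs, so the error is directional. The cause is visible in the counts: with 300 or 600 events the last window has 9 or 18, below the 25 needed. The rates shift with set-up; other versions of the same scenario gave 78%/43%/10% (12 windows) and 82%/56%/19%.

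Same constant VE 67.8% with level events: first significant and last not in 22%, 5% and 0.1% of runs. The reverse pattern is equally frequent, so with level events the pattern shows only low power per window.

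Real waning (VE 67.8% to 30%, 13 windows, level events): the first and last 95% CIs separate in 3%, 12% and 35% of runs at 300, 600 and 1,200 events. The trend contrast has power 40%, 75% and 97%.

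**Does the contrast survive delayed onset?** Take VE falling from 65% to 20% over 12 windows, but VE 0% in the first window. Power of a slope fitted from index falls from 55-57% to 9-13% at 30 events per window, and from 87-88% to 16-25% at 60, depending on set-up. Starting the slope after the first window restores it to about 43% and 76%.

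**The case against.** The strongest reply is that window HRs are themselves a piecewise estimate of effect over time, that the plan declares no hypothesis, and that a statistical analysis plan not shown here could add a summary contrast. Much of this stands. The display is valid, and the trend contrast above is computed from nothing more than the window HRs and their standard errors, so the planned output does not throw the information away. Nor does the protocol say that the windows are fitted in separate models. Switching to monthly windows depends on event counts, not on observed effects, and no bias from it has been shown.

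A reader might infer more: that reading the windows one by one inherently produces false waning, or that the plan runs a test with an uncontrolled error rate. The documents support neither. No reading rule is stated and no test is claimed. With level events, significance is lost early as often as late. The directional error needs both thinning later windows and a reading based on lost significance.

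What does not stand is that this is a detail left for later. Section 8.8.3 fixes the Objective 2 method, and that method stops one step short of the objective. An estimation study with no hypothesis still needs an estimate of its target quantity with an interval.

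A further fair objection is that a term linear from the index date mixes onset of protection with waning. The last calculation confirms this, and the fix below is shaped by it.

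**Conclusion.** The gap is real and modest. Objective 2 has a descriptive display but no estimate or confidence interval for the change in HR with time since the 4th dose. Objective 1 is unaffected.

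How much this could mislead cannot be fixed from the protocol, because it gives no event counts and no reading rule. With a five-fold fall in events and a reading based on lost significance, a constant VE of 67.8% looks like waning in 80% of studies at 300 total events but 12% at 1,200. With level events the pattern has no direction, and at about 92 events per window (1,200/13) and VE 67.8% it nearly disappears. A contrast is no cure for sparse data either: at 300 events its power for a fall from 67.8% to 30% is 40%. It would report that uncertainty openly as a wide interval.

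**What to change.** In 8.8.3, keep the bi-weekly or monthly HRs and the plots as descriptive display, and add one pre-stated contrast from a Cox model over the matched follow-up. Either form will do:

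- a 4th-dose by time-since-index term, reported as the ratio of HRs per 4 weeks; or
- an early-versus-late ratio of HRs with both periods named.

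Report it with a 95% CI and pool it across databases as in section 8.9. Start it after a pre-specified initial window so that onset of protection is not counted against waning. State that waning is judged from this contrast and not from individual windows losing significance.

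The cost is one model term in the existing code and a few sentences, on the same cohorts and data. The small downside is that the form of the decline and the starting window must be chosen in advance; the window HRs remain as a check on linearity.
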